11.7 COLUMBIA-SUICIDE SEVERITY RATING SCALE

For the C-SSRS, the number and percentage of patients with suicidal ideation or suicidal behavior, as recorded on the C-SSRS scale, will be presented. The distribution of response for most severe suicidal ideation and suicidal behavior during the lifetime history, the OLTP, and the DBTP will be presented. Supportive listings will be provided, including the PID number, treatment group (for DBTP only), visit number, lifetime history, and postbaseline values for each patient. Intensity of ideation, suicidal behavior type, and lethality of suicidal behavior will also be included in these listings. Listings of all AEs occurring in patients who have suicidal ideation or suicidal behavior during OLTP and during DBTP will also be provided.

11.7.1 Extrapyramidal Symptom Scales

A patient will be considered to have treatment-emergent parkinsonism if the patient's SAS score was ≤ 3 at baseline and > 3 at any postbaseline assessment. A patient will be considered to have treatment-emergent akathisia if the patient's BARS score was ≤ 2 at baseline and > 2 at any postbaseline assessment. The number and percentage of patients with treatment-emergent parkinsonism or akathisia will be tabulated. Listings of patients with treatment-emergent parkinsonism or akathisia will be provided, including the PID number, baseline and postbaseline values. Listings of all AEs for patients with treatment-emergent parkinsonism or akathisia will also be provided.

Descriptive statistics (n, mean, SD, minimum, median, and maximum) for EPS scale parameters (AIMS, BARS, and SAS) and changes from baseline values at each assessment timepoint in this study will be presented overall for the OLTP and by treatment group for the DBTP.

12.0

HEALTH OUTCOMES ANALYSES

Not applicable.

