6.7 DOUBLE-BLIND INTENT-TO-TREAT POPULATION

The DB ITT population will consist of all patients who took at least 1 dose of DB IP and had at least 1 post-randomization assessment of the PANSS or CGI-S scores during the DBTP of the study.

Patients will be included in the randomized treatment group for the DB ITT population.

7.0**STUDY PATIENTS****7.1****PATIENT DISPOSITION**

The OLTP starts with the first dose of OLTP and ends with one of the following: the last scheduled assessment at the Visit 13/end of OLTP (Week 18) or early termination (ET) before Visit 13 (Week 18) for patients who do not enter the DBTP; or 1 day before the first dose of DBTP (or the date of the first dose of the DB IP if the last scheduled assessment date in the OLTP is on the date of the first dose of the DBTP) for patients who enter the DBTP.

The DBTP starts with the first day of randomization and ends with the last scheduled assessment at Visit 26 (Week 44) or ET.

The SFU period starts one day after the end of the previous period and ends with the last available assessment. For patients without Visit 27 (Week 46) or Visit 28 (Week 48) assessment, the SFU period would not be derived.

Screen-failure patients (ie, patients screened but not included in the OL Safety Population) and the associated reasons for failure will be tabulated overall for the Screened Population.

The number and percentage of patients in the Screened, OL Safety and OL ITT Populations will be summarized overall and by study center. The number and percentage of patients in the Randomized, DB Safety, and DB ITT Populations will be summarized overall by treatment group and by treatment group and study center.

The number and percentage of patients in the OL Safety Population, who prematurely discontinued from the OLTP, who completed the OLTP, who entered the DBTP, and who entered the SFU period will be summarized overall and by reasons for premature discontinuation as recorded on the respective disposition pages of the electronic case report form (eCRF).

Similarly, the number and percentage of patients in the DB Safety Population who completed the DBTP, who prematurely discontinued from the DBTP, and who entered the SFU period will be summarized overall, by DB treatment group and by reasons for premature discontinuation as recorded on the respective disposition pages of the eCRF. Patients who relapse during the DBTP will also be summarized as completing the study.

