11.0 SAFETY ANALYSES

The safety analyses will be performed for the OL safety, OL SFU and DB safety populations. The summarization will be overall for the OLTP in the OL safety population and OL SFU period in the OL SFU population, and by treatment group for the DB period and the DB SFU period in the DB safety population. The summarization for the OLTP will use the OL safety population as the denominator. The summarization for the DBTP will use the DB safety population as the denominator. The summarization for the OL SFU period or DB SFU period will use the OL SFU population or the DB safety population as the denominator respectively.

Safety parameters will include adverse events (AEs), clinical laboratory parameters, vital signs, Electrocardiographic (ECG) parameters, ophthalmological parameters, Columbia–Suicide Severity Rating Scale (C-SSRS), and EPS scales, including Abnormal Involuntary Movement Scale (AIMS), Barnes Akathisia Rating Scale (BARS), and Simpson-Angus Scale (SAS).

For each safety parameter, the last assessment made before the first dose of OL IP will be used as the baseline for all analyses of that safety parameter, unless stated otherwise. Continuous variables will be summarized by number of patients and mean, SD, median, minimum, and maximum values. Categorical variables will be summarized by number and percentage of patients.

The derived visits in the DBTP will use the same strategy as described in Section 10.0. The detailed week mapping windows is provided in Section 16.1.

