Clinical laboratory test values will be considered potentially clinically significant (PCS) if they meet either the lower-limit or higher-limit PCS criteria listed in [Table 11-1](#). The number and percentage of patients who have PCS postbaseline clinical laboratory values will be tabulated overall for the OLTP, and by treatment group for the DBTP. The percentages will be calculated relative to the number of patients with available non-PCS baseline values and at least 1 postbaseline assessment for the corresponding periods (OLTP or DBTP). The numerator will be the total number of patients with available non-PCS baseline values and at least 1 PCS postbaseline value for the corresponding periods (OLTP or DBTP). A supportive tabular display of patients with PCS postbaseline values will be provided, including the PID number, study center number, and baseline and all postbaseline (including non-PCS) values.

In addition, a tabular display showing all AEs that occurred in patients who had PCS postbaseline clinical laboratory values will be provided.

Potential Hy's Law criteria within a 24-hour window is defined by a post baseline elevation of alanine aminotransferase (ALT) or aspartate aminotransferase (AST) $\geq 3x$ ULN, along with total bilirubin (TBL) $\geq 2x$ ULN and a non-elevated alkaline phosphatase (ALP) $< 2x$ ULN, all based on blood draws collected within a 24-hour period.

Patients who meet the potential Hy's Law criteria during the OLTP will be summarized for the OL Safety Population. Patients who meet the potential Hy's Law criteria from the first dose of DB IP to within 30 days after the last dose of DB IP will be summarized for the DB Safety Population. Supportive tabular displays will also be provided.

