16.0 DATA HANDLING CONVENTIONS

16.1 VISIT TIME WINDOWS

Table 16-1 presents the visits assigned for efficacy and safety analyses and the corresponding range of treatment days (window) during which an actual visit may occur.

Table 16-1 Visit Time Windows

Derived Visit	Open-label Period	
	Scheduled Visit Day Relative to the first dose of OL IP	Window
OL Baseline	Day 1	Days \leq 1
OL Week 1	Day 8	Days [2, 11]
OL Week 2	Day 15	Days [12, 18]
OL Week 3	Day 22	Days [19, 25]
OL Week 4	Day 29	Days [26, 35]
OL Week 6	Day 43	Days [36, 49]
OL Week 8	Day 57	Days [50, 63]
OL Week 10	Day 71	Days [64, 77]
OL Week 12	Day 85	Days [78, 91]
OL Week 14	Day 99	Days [92, 105]
OL Week 16	Day 113	Days [106, 119]
OL Week 18	Day 127	120 \leq days \leq the day of the last visit during the OL period*
End of the OL Period ^a	Last Assessment during the OL	
Double-blind Period		
	Scheduled Visit Day Relative to the first dose of DB IP	Window
	Day 1	Days \leq 1
DB Baseline (for efficacy endpoints only)	Day 15	Days [2, 21]
DB Week 2	Day 29	Days [22, 35]
DB Week 4	Day 43	Days [36, 49]
DB Week 6	Day 57	Days [50, 63]
DB Week 8	Day 71	Days [64, 77]
DB Week 10	Day 85	Days [78, 91]
DB Week 12	Day 99	Days [92, 105]
DB Week 14	Day 113	Days [106, 119]

Derived Visit	Open-label Period	
	Scheduled Visit Day Relative to the first dose of OL IP	Window
DB Week 18	Day 127	Days [120, 133]
DB Week 20	Day 141	Days [134, 147]
DB Week 22	Day 155	Days [148, 161]
DB Week 24	Day 169	Days [162, 175]
DB Week 26	Day 183	176 ≤ days ≤ the day of the last visit during the DB period
End of the DB period^a	Final or Termination Visit during the double-blind treatment period	
	Safety-follow-up (SFU) Period^b	
	Scheduled Visit Day Relative to the start of SFU	Window
SFU Week 2 ^b	Day 15	+1 ≤ days ≤ 21
SFU Week 4 ^b	Final or Termination Visit of the study after day 21 .	

OL Day 1 = the date of the first dose of open-label investigational product;

DB Day 1 = the date of the first dose of double-blind investigational product. There is no Day 0.

a Presented in analysis tables for safety parameters, including but not limited to electrocardiograms, clinical laboratory values, and vital signs.

b Presented in analysis tables for vital signs.

OL = Open Label; DB = Double-blind; SFU = Safety Follow-up; ET = Early Termination; IP = Investigational Products.

* All the available OL week 18/visit 13 Ophthalmological examination will be mapped to the OL safety period.

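### By-arm double-blind counts of treatment-emergent parkinsonism and akathisia mix new cases with persisting open-label cases, because the baseline precedes open-label treatment

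*SAP*

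**What the plan says.** SAP 11.7.1 defines treatment-emergent parkinsonism by "SAS score was ≤ 3 at baseline and > 3 at any postbaseline assessment" and treatment-emergent akathisia by "BARS score was ≤ 2 at baseline and > 2 at any postbaseline assessment". It then says: "The number and percentage of patients with treatment-emergent parkinsonism or akathisia will be tabulated". That sentence names no period, arm or denominator. Protocol 7.3.4.5.1 has the same rules.

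The baseline comes from SAP 11.0: "the last assessment made before the first dose of OL IP will be used as the baseline for all analyses of that safety parameter". The rule allows stated exceptions, and Protocol 7.3.4 agrees. Neither EPS section states one, and SAP Table 16-1 labels its only randomization baseline "DB Baseline (for efficacy endpoints only").

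SAP 11.0 also sets the general layout: overall for the OL period, and "by treatment group for the DB period and the DB SFU period in the DB safety population". The laboratory rule in SAP 11.2 names the period in its numerator ("at least 1 PCS postbaseline value for the corresponding periods (OLTP or DBTP")). The vital-sign and ECG rules in SAP 11.3 and 11.4 do the same. The EPS count does not.

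**The concern.** Every randomized patient, including those assigned to placebo, has first taken OL cariprazine. By Protocol 6.5.8.1 the EPS scales are rated at Visits 3, 7, 9, 11 and 13 after OL dosing has begun. All of these are postbaseline ratings under the SAP's definition. A patient can therefore become a case before randomization and carry that status into a DB arm.

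Nothing keeps such patients out. Protocol 4.6 asks for ability to tolerate 4.5 mg/d safely and sets no SAS or BARS limit, and Protocol 4.8.3.2 allows rescue drugs for EPS. Entry is also open at the other end: exclusion criterion 11 removes only patients whose EPS needs drug treatment at Visit 2, so some may start above a cut-off.

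The stake is the tolerability comparison. Protocol section 1 gives placebo a central role in interpreting the safety findings. It also plans, if both doses prove effective, to ask whether the lower one is better tolerated in maintenance. A by-arm count that cannot separate new EPS from EPS that has not yet resolved answers that question poorly.

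**Working it through.** **Who is counted.** Apply the OL baseline and assume, as SAP 11.0 implies, that the DB table uses DB-period ratings only.

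| OL baseline | During OL | Visit 13 | On DB treatment | Counted in DB arm? | New on DB treatment? |
|---|---|---|---|---|---|
| at/below cut-off | at/below | at/below | above | yes | yes |
| at/below | above | above | above | yes | no |
| at/below | above, resolved | at/below | at/below | no | no |
| above | any | at/below | above | never | yes, relative to Visit 13 |

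The second row adds persisting cases, and the fourth loses new ones.

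**Size.** The plan states no figure to reproduce. The one documented input is 115 planned per arm (Protocol 4.1). The rest is assumed:
- q = share of randomized patients who crossed the cut-off in OL, equal across arms by randomization: 5, 10 or 20%. Tolerability screening before randomization favours the low end.
- d = share of the remainder who first cross on DB treatment: 6% (4.5 mg/d), 3% (3.0 mg/d), 2% (placebo).
- π = share of OL-onset cases still above the cut-off at one or more DB ratings.

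Counted proportion in an arm = qπ + (1 − q)d.

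*Equal persistence, π = 50% in every arm:*

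| q | 4.5 | 3.0 | Placebo | Ratio 4.5:3.0 | Difference 4.5 − 3.0 | New-case part, (1 − q) × 3 |
|---|---|---|---|---|---|---|
| 5% | 8.20% | 5.35% | 4.40% | 1.53 | 2.85 | 2.85 |
| 10% | 10.40% | 7.70% | 6.80% | 1.35 | 2.70 | 2.70 |
| 20% | 14.80% | 12.40% | 11.60% | 1.19 | 2.40 | 2.40 |

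For example, at q = 5% on 4.5 mg/d: 0.05 × 0.5 + 0.95 × 0.06 = 0.082. Among patients without OL onset the ratio is 6/3 = 2.0. Persisting cases number 115 × q × 0.5 = 2.9, 5.8 or 11.5 per arm. Their share of the placebo count, qπ divided by the count, is 2.5/4.4 = 57%, 5/6.8 = 74% or 10/11.6 = 86%. The term qπ is the same in both dose arms and cancels from the difference, so only the ratio is diluted.

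If resolved OL cases are instead put back at risk, the formula becomes qπ + (1 − qπ)d. The ratios are then 8.35/5.425 = 1.54, 10.7/7.85 = 1.36 and 15.4/12.7 = 1.21, so this choice matters little.

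*Unequal persistence, π = 75/50/25% on 4.5/3.0/placebo:*

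| q | 4.5 | 3.0 | Placebo | Difference 4.5 − 3.0 | From new cases | From persistence, q × 25 |
|---|---|---|---|---|---|---|
| 5% | 9.45% | 5.35% | 3.15% | 4.10 | 2.85 | 1.25 |
| 10% | 12.90% | 7.70% | 4.30% | 5.20 | 2.70 | 2.50 |
| 20% | 19.80% | 12.40% | 6.60% | 7.40 | 2.40 | 5.00 |

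The difference now combines onset with resolution, and the table gives no means of telling them apart.

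The fourth row of the first table is not sized. The documents do not say how many patients enter above a cut-off.

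**The case against.** The OL baseline is prespecified in both documents and matches the treatment-emergent adverse event definition, which also runs from the first OL dose. EPS present during maintenance matters to patients whenever it began, and faster resolution after a dose reduction is a real treatment effect. On that view the planned count estimates prevalence in the period, and a new-onset count answers a different question. This stands, and it is why the planned count should be kept and supplemented.

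Three further points also stand:
- With equal persistence the risk difference is not distorted.
- SAP 4.0 puts table specifications in a separate document, which may name the period. The listings in SAP 11.7.1 would let a reader sort cases by hand.
- The study was terminated early, and SAP Appendix IV includes no EPS-scale table or listing.

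A reader might go further than the text allows in three ways.
- **Resolved OL cases counted in DB arms.** Taken alone, the any-postbaseline wording suggests it. But the by-arm layout comes only from SAP 11.0, which ties arm to the DB period in the same sentence. Taking the arm without the period is not a consistent reading.
- **Visit 13 ratings falling in both periods.** SAP 7.1 says "The DBTP starts with the first day of randomization", and the OL period can end on the first DB dosing date. But SAP 7.1 extends the OL period to cover a last OL assessment on that date. Table 16-1 opens the first DB post-baseline window on Day 2, so a pre-dose Visit 13 rating maps to OL.
- **All carried-over cases arising on 4.5 mg/d.** The Visit 3 rating follows a week on 1.5 mg/d, so onset may be at any titration dose.

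**Conclusion.** The point holds in a limited form. SAP 11.7.1 does not name the period, and the only applicable baseline precedes OL treatment. Even with the DB table confined to DB ratings, persisting OL-onset cases count as emergent in every arm, and patients above the cut-off at OL baseline can never count.

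That conclusion follows from the text. Its size rests entirely on the assumed rates. Ratios between doses shrink from 2.0 to between 1.53 and 1.19 when half the OL cases persist in each arm, and the risk difference is then untouched. If persistence falls with dose, the difference reads 4.1 to 7.4 points, of which new cases supply 2.85 to 2.4. It would be wrong to infer that the dose contrast is biased on every scale or in a known direction.

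The outputs are descriptive, and the EPS part affects only the full SAP analysis. The live output is the DB-period laboratory table of potentially clinically significant (PCS) values, which Appendix IV keeps. It has the period limit but the same OL baseline, so abnormalities that arose in OL and persist count there too. No size can be given for that table. This is a cheap improvement of low priority.

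**What to change.** In SAP 11.7.1:
- Add the period wording already used in SAP 11.2, 11.3 and 11.4.
- Keep the OL-baseline DB count, labelled as such. Beside it give a by-arm count of new cases: patients at or below the cut-off at the last assessment before the first DB dose, with only later DB-period ratings used. The denominator is such patients with at least one later DB rating.
- Add one line per arm for patients above the cut-off at Visit 13, and how many remain above it at their last DB-period assessment.

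In the DB-period laboratory PCS table, including the Appendix IV version, add a by-arm line restricted to patients who were non-PCS at Visit 13.

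The cost is SAP wording, one baseline flag and a few table rows. No new data are needed, because Protocol 8.4.4 already collects the EPS scales and laboratory samples at Visit 13. The baseline rule in both documents allows exceptions that are stated, so no protocol amendment is required. The downsides are two baselines that must be clearly labelled and slightly smaller denominators. In the abbreviated report only the laboratory line changes, unless EPS-scale tables are added to Appendix IV.

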13.0 INTERIM ANALYSIS

No interim analysis is planned for this study.

14.0 DETERMINATION OF SAMPLE SIZE

The sample size and power calculations are based on the analysis of time to relapse in the DBTP to compare each cariprazine dose group versus placebo using a log-rank test. The trial will be a fixed follow-up design. Patients are followed from randomization until dropout, relapse or a fixed duration of 26 weeks.

Based on the results from RGH-MD-06, the relapse hazard ratio is assumed to be 0.50, and cumulative relapse rate at Week 26 for the placebo group is 46% (Study RGH-MD-06, 2015). In addition, the cumulative dropout rate due to reasons other than relapse at 26 weeks is assumed to be 20%.

Using these assumptions, a total of approximately 103 relapse events in the DB period need to be observed in order to have 85% power to detect a statistically significant difference between each cariprazine and placebo group, using 2-tailed, log-rank tests at an overall 5% level of significance. The trial should randomize approximately 345 patients, 115 patients each arm, to provide the required number of relapse events. EAST 6.0 was used for sample size and power calculation.

A fixed-sequence procedure will be used for multiple comparisons to control the family-wise Type I error rate at a 0.05 level. First, the cariprazine 4.5 mg/d group will be compared with the placebo group in the primary endpoint; if the test for cariprazine 4.5 mg/d versus placebo is significant at the 0.05 level, then cariprazine 3.0 mg/d arm will be tested versus placebo at 0.05 level.

Assume the screening failure rate is 34%, and approximately 33.3% of patients enrolled into the OLTP will be randomized into the DBTP. Then, approximately 1035 patients will be expected to be enrolled into the OLTP, and approximately 1569 patients are expected to be screened.

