[figure not shown]
The fixed-sequence testing procedure will be used for multiple comparisons to control the family-wise Type I error rate at a 0.05 level. The comparison of cariprazine 4.5 mg/d versus placebo will be tested first at a 0.05 significance level, only when the testing is significant, the comparison of cariprazine 3.0 mg/d versus placebo will be tested.

All safety parameters will be analyzed descriptively.

Sample Size Calculation:

The sample size and power calculations are based on the analysis of time to relapse in the DB treatment period to compare each cariprazine dose group versus placebo based on a log-rank test.

Based on the first 26 weeks' data from RGH-MD-06, the relapse hazard ratio is assumed to be 0.50, and cumulative relapse rate at Week 26 for the placebo group is 46%. In addition, the cumulative dropout rate due to reasons other than relapse at 26 weeks is assumed to be 20.0%. A total of approximately 103 in the DB treatment period need to be observed in order to have 85% power to detect a statistically significant difference between each cariprazine and placebo group, using two-tailed, log-rank tests at a 5% level of significance. The study should randomize approximately 345 patients, 115 patients each arm, to provide the required number of relapse events. Given the fixed-sequence testing strategy, the higher dose of 4.5 mg/d has 85% statistical power to show significance versus placebo, and the 3.0 mg/d dose, would also have an 85% power provided that testing for cariprazine 4.5 mg/d group is statistically significant. EAST 6.0 was used for power and sample size calculation.

Figure 1: Study Schematic

Note: Patients will receive open-label cariprazine dosed as 1.5 mg/d beginning at Visit 2 (Baseline); titrated to 3.0 mg/d at Visit 3 (end of Week 1), and then titrated to 4.5 mg/d at Visit 4 (end of Week 2). Patients will continue on the 4.5 mg/d dose for the remainder of the open-label treatment period.

Table 1: Schedule of Visits and Procedures—Screening/Washout and Open-label Treatment Periods

Study Period	Screening/Washout Period		Open-label Treatment Period										13/End of OL
	1/ Screening	2/ Baseline	3	4	5	6	7	8	9	10	11	12	
Visit Number/Visit Title	Up to 7 days (Days -7 to -1)	0 (1)	1 (8)	2 (15)	3 (22)	4 (29)	6 (43)	8 (57)	10 (71)	12 (85)	14 (99)	16 (113)	18 (127)
End of Study Week (Day)													
Visit Window (Days)	+3	±3	±3	±3	±3	±3	±3	±3	±3	±3	±3	±3	±3
Informed Consent	X												

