7.5 Sample Size Calculation

The sample size and power calculations are based on the analysis of time to relapse in the DB treatment period to compare each cariprazine dose group versus placebo based on a log-rank test. The trial will be a fixed follow-up design. Patients are followed from randomization until dropout, relapse or a fixed duration of 26 weeks.

Based on the first 26 weeks' data from RGH-MD-06, the relapse hazard ratio is assumed to be 0.50, and cumulative relapse rate at Week 26 for the placebo group is 46% (Study RGH-MD-06, 2015). In addition, the cumulative dropout rate due to reasons other than relapse at 26 weeks is assumed to be 20.0%.

Using these assumptions, a total of approximately 103 in the DB phase need to be observed in order to have 85% power to detect a statistically significant difference between each cariprazine and placebo group, using 2-tailed, log-rank tests at an overall 5% level of significance. The trial should randomize approximately 345 patients, 115 patients each arm, to provide the required number of relapse events. EAST 6.0 was used to for sample size and power calculation.

A fixed-sequence procedure will be used for multiple comparisons to control the family-wise Type I error rate at a 0.05 level. First, the cariprazine 4.5 mg/d group will be compared with

the placebo group in the primary endpoint; if the testing is significant at the 0.05 level, then cariprazine 3.0 mg/d arm will be compared with the placebo group.

Assume the screening failure rate is 34%, and approximately 33.3% of patients enrolled into the OL treatment period will be randomized into the DB treatment period. Then, approximately 1035 patients will be expected to be enrolled into the OL treatment period, and approximately 1569 patients are expected to be screened.

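### The plan states 85% power for each dose, but under its own fixed sequence the chance of a significant 3.0 mg/d result is about 75%

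*SAP*

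**What the plan says.** SAP 14.0 bases the sample size on a log-rank comparison of each dose with placebo. It assumes a hazard ratio of 0.50, 46% placebo relapse at Week 26 and 20% dropout for other reasons. It then asks for about 103 relapse events "in order to have 85% power to detect a statistically significant difference between each cariprazine and placebo group", and for 345 patients, 115 per arm. It describes the testing level in these words: "using 2-tailed, log-rank tests at an overall 5% level of significance". Protocol 7.5 makes the same claim: the events "need to be observed in order to have 85% power to detect a statistically significant difference between each cariprazine and placebo group".

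The next paragraph of each section sets the fixed sequence. In the SAP, "if the test for cariprazine 4.5 mg/d versus placebo is significant at the 0.05 level, then cariprazine 3.0 mg/d arm will be tested". Protocol 7.5 has the same gate: 3.0 mg/d is compared with placebo "if the testing is significant at the 0.05 level" for 4.5 mg/d.

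Only the Protocol Summary ties the 3.0 mg/d power to the gate. There, "the 3.0 mg/d dose, would also have an 85% power provided that testing for cariprazine 4.5 mg/d group is statistically significant".

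The event count is also loosely worded. Protocol 7.5 says "a total of approximately 103 in the DB phase need to be observed" and the Protocol Summary says "A total of approximately 103 in the DB treatment period need to be observed"; neither says what is being counted. SAP 14.0 supplies the missing noun. None of the three says whether 103 covers two arms or three.

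**The concern.** Under a fixed sequence the second hypothesis can be declared significant only if the first one is. The power for 3.0 mg/d is therefore the probability that both tests succeed, and this is below the power of either test alone unless the two statistics are perfectly correlated. A single 85% for each dose, placed beside the gate and described as being at an overall 5% level, invites the reader to take 85% as the chance of a significant 3.0 mg/d result.

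The 3.0 mg/d comparison is the study's second objective and carries the dose-reduction question. Someone reading SAP 14.0 or Protocol 7.5 alone would put the risk of missing a true effect there at 15%. Under the plan's own assumptions it is about 25%.

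**Working it through.** **Inputs** (SAP 14.0; Protocol 7.5 agrees): two-sided alpha 0.05; hazard ratio 0.50, the only value given, so applied to both doses; placebo relapse 46% at 26 weeks; dropout 20% at 26 weeks; fixed 26-week follow-up; 115 per arm. Exponential relapse and independent exponential dropout are my assumptions, since the plan does not name its distributions.

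**Step 1: reproduce the plan's figures.**

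- Weekly hazards: placebo −ln(0.54)/26 = 0.02370; cariprazine half of that, 0.01185; dropout −ln(0.80)/26 = 0.00858.
- Probability of an observed relapse = λ/(λ+η) × [1 − exp(−26(λ+η))], with λ the relapse hazard and η the dropout hazard. This gives 0.4170 on placebo and 0.2390 on each cariprazine arm.
- Expected events: 115 × 0.4170 = 47.95 on placebo; 115 × 0.2390 = 27.49 per cariprazine arm.
- Per comparison: 47.95 + 27.49 = 75.44. Over three arms: 47.95 + 2 × 27.49 = 102.93.
- Events needed per comparison (Schoenfeld): 4 × (1.960 + 1.036)² / (ln 0.5)² = 74.7.
- Pairwise power: Φ(ln 2 × √(75.44/4) − 1.960) = Φ(1.050) = 0.853.

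The 345 patients, 103 events and 85% all reproduce, provided that 103 is the three-arm total. Read as events per comparison, 103 would give 94.0% power.

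**Step 2: power for 3.0 mg/d under the sequence.** Treat the two test statistics as bivariate normal, each with power 0.853, correlated through the shared placebo arm. The event counts suggest a correlation of 27.49/75.44 = 0.364. The simulation below gives 0.51, so 0.5 is the better approximation.

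| Correlation | Both tests significant | 3.0 mg/d given 4.5 mg/d significant |
|---|---|---|
| 0 (independent) | 72.8% | 85.3% |
| 0.364 | 75.1% | 88.1% |
| 0.5 | 76.2% | 89.4% |

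**Step 3: simulation.** In 40,000 simulated three-arm trials analysed with the actual log-rank tests:

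- mean total events 102.9;
- 4.5 mg/d significant in 84.4%;
- 3.0 mg/d significant, ignoring the gate, in 84.3%;
- both significant in 74.8%;
- conditional power for 3.0 mg/d 88.7%;
- correlation of the two statistics 0.51.

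**Gap.** Like for like, it is 85.3 − 76.2 = 9.1 points by formula at correlation 0.5, and 84.4 − 74.8 = 9.6 points by simulation. Against the stated 85%, the simulated figure is 10.2 points lower.

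**The case against.** The strongest reply is that no number is wrong. Both sections open by describing pairwise comparisons with placebo, and 85% is the correct pairwise power. The gate appears in the very next paragraph, and nothing there says that 85% is the probability of passing it. The Protocol Summary already conditions the 3.0 mg/d figure. On this view the point is one of reporting, and a small one in a trial that was stopped.

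Much of this stands. Sample size, event count and Type I error control are unaffected. The Protocol Summary's 85% is slightly conservative as a conditional figure, since the calculation gives about 88% to 89%. The 103 reads fairly naturally as a study total, and the missing noun is a drafting slip. The exact gap depends on the method, at about 9 to 10 points.

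It does not remove the point. Neither section labels the 85% as pairwise or marginal, and the condition in the Protocol Summary is repeated in neither. A conditional figure also does not tell the reader how likely a significant 3.0 mg/d result is, and no section does. As for early termination (SAP 4.0 and Appendix IV), the amended SAP that reports it still carries section 14.0, and Appendix IV keeps the primary efficacy analysis in the abbreviated report.

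**Conclusion.** The concern holds. The unconditional 85% in SAP 14.0 and Protocol 7.5 is right for 4.5 mg/d but overstates the power for 3.0 mg/d under the stated testing rule, which is about 75%.

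This rests on a hazard ratio of 0.50 at both doses, exponential relapse and dropout, and the planned 115 per arm. Over correlations from 0 to 0.5 the formula gives 73% to 76%, so the conclusion does not depend on the exact correlation. A weaker effect at 3.0 mg/d would lower the figure further. Because the study ended early, the point concerns the record of planned power, not the conduct or analysis of the trial.

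**What to change.** In SAP 14.0 and Protocol 7.5, and for consistency in the Protocol Summary, replace the power statement with wording such as:

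> About 103 relapses over all three arms (about 75 in each cariprazine–placebo pair) provide 85% power for 4.5 mg/d against placebo. With the fixed sequence, and a hazard ratio of 0.50 at both doses, power for 3.0 mg/d against placebo is about 75% (about 88% to 89% once 4.5 mg/d is significant).

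This also supplies the missing noun and the three-arm label for 103. The cost is one or two sentences in three places, and a less favourable stated figure for 3.0 mg/d. Sample size, test order, alpha and analysis do not change.
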